Study outcomes	
The main outcomes of this study are
 
 1) The change of baseline glycated hemoglobin (HbA1c) among prediabetes adults at 6 months. 2) The change of baseline fasting plasma glucose (FPG) among prediabetes adults at 6 months. 3) The change of baseline 2-hour post-load plasma glucose among prediabetes adults at 6 months. 4) The change of baseline continuous glucose monitoring (CGM) profile among prediabetes adults at 6 months. 
Secondary outcome of this study are
 
 1) The change of eating misalignment among prediabetes adults at 6 months. 2) The change of chronotype among prediabetes adults at 6 months.
Sample Size	120 prediabetic individuals
Study Duration	1 March 2022 until 31 December 2023
Name and Address of Sponsor	Fundamental Research Grant Scheme (FRGS), Ministry of Higher Education/ UMalaya (FRGS/1/2021/SKK06/TARUC/02/1)

Ethics Approval	Tunku Abdul Rahman University Management and Technology Ethics Committee (TAR UC/EC/2021/02-3) Medical Research and Ethics Committee (RSCH ID-21-00114-IVI)
-----------------	---

Executive Summary:

Early meal timing affects the circadian rhythmicity and influenced the postprandial blood glucose level in response to meal in diabetes patients. In the other words, diabetes patients with earlier meal timing had a stable glycemic control compared with those with late meal timing. This is a new concept to switch the meal timing earlier than later in diabetes self-monitoring management. However, there is insufficient evidence from Southeast Asia to determine the optimal-meal-timing and its association with glycemic measures in prediabetes individuals. Hence, this study carried out to determine the associations of chronotype and chrononutrition with glucose tolerance among prediabetic individuals in Malaysia.

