In Malaysia, there are no specific guideline for prediabetes individual and they are managed according to the latest Clinical Practice Guideline in Malaysia (MOH *et al.*, 2020). For prevention prediabetes to further develop to diabetes, lifestyle intervention such as weight loss (5-10% of initial body weight), regular physical activity (150 min/week), with dietary strategies including reduced calories and behavior modification are recommended in Clinical Practice Guideline in Malaysia (MOH *et al.*, 2020). A high fibre diet (20-30g/day with 5 to 7 servings/day) consisting of vegetables, fruits, legumes and whole grains is encouraged too (MDES, 2020). All the prediabetic individuals will be referred to dietitian and nurse educators for 6 months routine treatment, prior to T2DM diagnosis, determined by second-round of oral glucose tolerance test (OGTT) in 6-month period (MOH *et al.*, 2020). To the puzzlement of many diabetes researchers and clinicians, some of the prediabetes cases showed tremendous improvement in their blood sugar result, yet some of the prediabetes

individuals developed full-blown of T2DM with their blood sugar result higher than the normal range; despite all of them followed the same routine treatment from healthcare clinics. Perhaps, besides the usual routine treatment from Clinical Practice Guideline (MOH *et al.*, 2020) (weight management, physical activity advices and dietary modification); prediabetic individuals who able to improve their blood sugar result in 6-month period has particular meal-timing, compared to those has uncontrolled blood sugar result in 6-month period.

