Those who meet the inclusion criteria will be invited to participate in this study. Eligible participants shall meet all the following inclusion criteria.

- 1) Newly diagnosed prediabetic individuals who have been first seen by clinical dietitian registered under the Ministry of Health Malaysia.
- 2) Malaysian ≥ 18 years old.
- 3) Those who plan to continue prediabetes care at a community clinic in Melaka.
- 4) Those who can read, write and understand the Malay Language.

Participants who meet the following criteria will be excluded from continuing the study.

- 1) Night shift workers at least 3 times per week.
- 2) Known sleep disorder.
- 3) Pregnant Women.
- 4) Those on oral glucose-lowering medications, diabetes supplements, anticonvulsant medications or oral steroids currently or in the last month.
- 5) Those with prior explored to any information regarding time-of-eating/time-of-activity restriction.
- 6) Those with chronic kidney disease. They are excluded as current research lack of evidence to support the accuracy of using 24-hour continuous glucose monitoring system (CGMS) (Freestyle Libre Pro, Abbott, Germany).

Prediabetes and diabetes will be defined according to the latest Clinical Practice Guideline in Malaysia (WHO & IDF, 2006; ADA, 2020; MOH *et al.*, 2020). Diagnosis must be confirmed by measurement of venous plasma glucose (FBG and OGTT) or HbA1c level. Table 1 shows the diagnostic value for diabetes on plasma glucose. Table 2 shows the diagnostic values for prediabetes and diabetes based on OGTT. Table 3 shows the diagnostic values for prediabetes and diabetes based on HbA1c. All the tables are adapted from the Clinical Practice Guideline in Malaysia (WHO & IDF, 2006; ADA, 2020; MOH *et al.*, 2020).

Table 1 The diagnostic value for diabetes on plasma glucose

	Fasting	Random
Venous Plasma Glucose	≥ 7.0 mmol/L	≥ 11.1 mmol/L

In symptomatic individual, one abnormal glucose value is diagnostic.

In asymptomatic individual, 2 abnormal glucose value are required.

Table 2 The diagnostic values for prediabetes and diabetes based on OGTT

OGTT Plasma Glucose Values (mmol/L)		
Category	0 hour	2- hour
Normal	<6.1	<7.8
IFG	6.1-6.9	
IGT	-	7.8-11.0
DM	≥ 7.0	≥ 11.1

IFG= impaired fasting glucose; IGT=impaired glucose tolerance; DM=diabetes mellitus

Table 3 The diagnostic values for prediabetes and diabetes based on HbA1c

	Normal	Pre-diabetes	Diabetes
A1c	<5.6% (38mmol/mol)	5.6-6.2% (38-44 mmol/mol)	≥6.3% (45mmol/mol)

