research assistant using the following questionnaire including (1) Munich Chronotype Questionnaires (MCTQ) (Appendix D), (2) Pittsburgh Sleep Quality Index Questionnaire (PSQI) (Appendix H), (3) Harvard Light Exposure Questionnaire (HLEQ) (Appendix G), (4) International Physical Activity Questionnaire (IPAQ) (Appendix C) and (5) Chrononutrition Profile Questionnaire (CPQ) (Appendix I). Anthropometry measurements including body fat, height, body fat percentage, visceral fat, waist circumference and hip circumference will be measured. Participants are requested to fill up 3-days dietary record (3DDR) (2 weekdays and one weekend day) and the data will be collected in the next visit. Baseline reading of fasting plasma glucose (FPG, OGTT, liver function, and HbA1c) will be retrieved from medical records in the community clinic. Routine treatment will be provided as usual. To minimize the loss of follow-up, phone conversations will be made to ensure the 3-days dietary data is completed.

At the second visit (three months from the baseline), all participants are required to wear a CGMS sensor at the back of their upper arms to measure the 24 hours glucose fluctuation over 14 consecutive days. 3DDR will be given to participants to record their consecutive 3 days dietary record and will be returned after 14 days. After 14 days, participants will return the CGMS sensor at the community clinic. Or alternative way of CGMS sensor collection by an assistant at the participant's home. All questionnaires will be interviewed by a trained research assistant again. Anthropometry measurements including body fat, height, body fat percentage, visceral fat, waist circumference and hip circumference will be measured repeatedly.

At the third visit (six months from the first visit), for FBG, OGTT and HbA1c test, all the readings will be retrieved by the research assistant from the medical record to document the glycemic outcome. The participants will be interviewed by the trained research assistant during all clinic visits using similar questionnaires. All anthropometry measurements (body fat, height, body fat percentage, visceral fat, waist circumference and hip circumference) will be conducted again. 3DDR will be given to record their 3 days dietary intake again and the record progress will be followed up through phone. The original 3DDR will be collected at the routine appointment.

Sample size Calculation:

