To investigate the association of physical activity (MET score and steps count), sedentary behaviors (MET score), sleep pattern (sleep duration), diet quality (distribution of total energy, carbohydrate, protein, and fat), and light exposure (timing responded to a different type of light) with glycemic outcome, the multivariable generalized linear model will be conducted. Meanwhile, anthropometric measures (body mass index, body fat, and waist circumference) will be categorized as either normal or overweight and obesity group, followed by using logistic regression to examine the association between anthropometry status and glycemic outcome (non-diabetes or diabetes). In addition, the glycemic outcome will be categorized into diabetes incidence (diabetes and non-diabetes) to determine the participants who had been diagnosed with diabetes at 6 months. A logistic regression test will be used to examine the association between early and late-night mealtime and diabetes incidence.

Quality control

To ensure that the database accurately reflects the data reported in the questionnaires, a pre-test will be carried out. The research assistant trained to conduct the study procedures included interviewing administrative questionnaires, CGMS device, 3 days dietary record, and pedometer. Monthly meetings are held with the principal

investigator to review study procedures and progression. A monthly report will be documented after the meeting.

Data monitoring and management

Participants are anonymized and assigned with a specific ID at study entry. To ensure accuracy and completeness of data entry, data are checked by identifying if there is any outlier or missing value. The data checking process is performed in the first, third and sixth month of the data collection, such that the experience gained can be used to train the research assistant for improvement. Paper documents are kept in a locked cabinet and electronic data are stored on password-protected computers which can only be accessed by research team members. All records will be kept for at least 5 years after completing the study. After 5 years, all papers will be shredded using an office shredder. Extra care should be taken with sensitive or confidential information and a secure paper destruction service bin used. Digital data will be destroyed by deleting or overwriting information and destroying the physical media, such as CD rom.

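### Read literally, the exclusion sentence and criterion 4 remove participants who start a glucose-lowering drug before the 6-month tests, which selects on the outcome; the plan should say that criterion 4 applies at enrolment

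*Combined protocol and SAP*

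**What the plan says.** In section 3, Description of Methodology, the inclusion list opens with "Eligible participants shall meet all the following inclusion criteria". The exclusion list follows directly and opens with "Participants who meet the following criteria will be excluded from continuing the study". Criterion 4 reads "Those on oral glucose-lowering medications, diabetes supplements, anticonvulsant medications or oral steroids currently or in the last month". Neither the sentence nor the criterion names a visit or date at which it is checked. Criterion 5 reads "Those with prior explored to any information regarding time-of-eating/time-of-activity restriction".

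The main outcomes in the synopsis are 6-month changes, for example "The change of baseline glycated hemoglobin (HbA1c) among prediabetes adults at 6 months". The Statistical Analysis section also forms a binary diabetes-incidence outcome "to determine the participants who had been diagnosed with diabetes at 6 months" and fits logistic regressions to it. For the third visit, the protocol says that "all the readings will be retrieved by the research assistant from the medical record to document the glycemic outcome".

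The visit descriptions do not re-check eligibility at 3 or 6 months. The plan gives no rule for a participant who starts a listed drug after baseline. Medication is not among the named covariates, and no method for missing outcomes is given.

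**The concern.** The exclusion sentence is about continuing in the study, and criterion 4 is about current or recent drug use. Someone who starts an oral glucose-lowering drug in month 4 satisfies both and, on the plain words, leaves. Starting such a drug plausibly follows worsening glycaemia, so the rule would drop people because of a consequence of the outcome under study.

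Two analyses are at stake. The regressions of glycaemia on meal timing would lose observations from the high end of the outcome, which flattens the slope. The diabetes-incidence models would lose events, and few are expected in the first place. The text also conflicts with itself, because the Statistical Analysis section needs people whom the exclusion sentence may remove.

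**Working it through.** **Inputs.** From Sample size Calculation: effect size 0.13, power 0.90, two-sided alpha 0.05, test of a single coefficient in multiple linear regression, 83 evaluable, 50% dropout. From section 2, heading 1.1 Prediabetes: 5.8% to 18.3% of people with prediabetes develop diabetes each year. Not in the documents: q, the share of progressors who start a listed drug before the 6-month tests. It is varied from 0 to 100%.

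**Step 1: the plan's own figure.** Noncentral t with noncentrality √(f²·N), df = N − k − 1, f² = 0.13 and k = 1 predictor. Power is 0.897 at N = 82 and 0.901 at N = 83, so 83 reproduces. Then 83 / (1 − 0.5) = 166, which equals the site total 56 + 55 + 55. The protocol calls 0.13 a β-coefficient, but 83 follows when it is entered as f². That is a separate matter, and f² = 0.13 is used here as planned.

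**Step 2: expected progressors.** Six-month risk h = 1 − (1 − yearly rate)^0.5.
- Low: 1 − 0.942^0.5 = 0.0294; 83 × 0.0294 = 2.4.
- High: 1 − 0.817^0.5 = 0.0961; 83 × 0.0961 = 8.0.

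Among 166 recruited the figures are 4.9 and 16.0.

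**Step 3: effect of removal.** Take standardised exposure and outcome as bivariate normal with r² = 0.13 / 1.13 = 0.115 (r = 0.339). Progressors are the top share h of the outcome, above cut-off c, with normal density φ at c. A share q of them is removed.
- Retained share: K = 1 − q·h.
- Retained outcome variance: v = [1 − q(h + cφ)] / K − (qφ / K)².
- Slope relative to truth: v / [1 − r²(1 − v)].
- Retained r² = 0.115 × that ratio; f² = r² / (1 − r²); n = 83·K, rounded; power as in step 1.

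Worked for q = 100%:
- Low: c = 1.889, φ = 0.0670, K = 0.9706, v = 0.8440 / 0.9706 − (0.0670 / 0.9706)² = 0.865. Ratio = 0.865 / (1 − 0.115 × 0.135) = 0.88.
- High: c = 1.304, φ = 0.1705, K = 0.9039, v = 0.6816 / 0.9039 − (0.1705 / 0.9039)² = 0.7185. Ratio = 0.7185 / (1 − 0.115 × 0.2815) = 0.74.

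| Share of progressors removed | Slope relative to truth (low / high rate) | Power (low / high) | Incident cases left of 83 (low / high) |
|---|---|---|---|
| 0% | 1.00 / 1.00 | 0.901 / 0.901 | 2.4 / 8.0 |
| 25% | 0.97 / 0.95 | 0.888 / 0.875 | 1.8 / 6.0 |
| 50% | 0.94 / 0.89 | 0.877 / 0.842 | 1.2 / 4.0 |
| 100% | 0.88 / 0.74 | 0.846 / 0.743 | 0 / 0 |

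A simulation of the same model with 4 million draws gave the same slope ratios, and power within 0.001.

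**The case against.** The best reply is that the list is an ordinary screening list, loosely worded. It sits directly after the inclusion criteria. Criterion 5 concerns exposure before the study and makes sense only at entry. The word participants carries no weight, because the inclusion sentence uses it for people not yet enrolled. No visit description re-checks eligibility. The plan to count diabetes at 6 months suggests that the authors expected to keep progressors. All of this stands, and it makes an entry-only intent plausible. It does not settle the matter, because no sentence limits the list to entry and site staff or analysts could apply it either way.

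The second reply concerns who is exposed. A reader might infer that everyone who progresses is removed, so that the worst outcomes are lost. The documents do not support that. Diabetes is not an exclusion criterion. The Introduction describes routine treatment "prior to T2DM diagnosis, determined by second-round of oral glucose tolerance test (OGTT) in 6-month period", so the diagnosing test would often be the 6-month outcome itself, recorded before any drug that follows from it. Only those who start a drug before the 6-month tests are exposed. Their number is unknown but need not be zero, since visits follow clinic schedules and routine treatment continues.

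A third reply, that the 50% dropout allowance covers such losses, does not stand. An allowance restores numbers; it does not correct a slope estimated after removal that depends on the outcome.

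**Conclusion.** The point holds as an ambiguity whose literal reading is harmful. Followed to the letter, the exclusion sentence and criterion 4 remove participants for a consequence of worsening glycaemia and contradict the diabetes-incidence analysis. The documents do not show that this removal is intended or would occur.

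The size runs from nothing to a ceiling of 12% to 26% loss of slope, power of 0.85 to 0.74 and an empty incidence outcome. That ceiling needs every progressor to start a listed drug before the 6-month tests and to be removed, so it should not be read as the expected effect. The incidence analysis is the more fragile: with 2.4 to 8.0 expected events, losing even a few matters.

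These figures assume that the quoted yearly rate applies evenly over the year and to this population, that progressors are the highest outcomes on a normal scale, and that f² = 0.13 with 83 completers. One part survives even if the list is entry-only: the plan does not say how 6-month values measured on a drug are to be analysed.

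**What to change.** These changes concern data retention and analysis only, not anyone's care.

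1. In the exclusion list, state that criterion 4 is applied at enrolment.
2. State that participants who start a listed medication afterwards stay in follow-up and in the analysis, with the start date recorded.
3. In Statistical Analysis, state that a clinic diagnosis of diabetes by 6 months counts as an event whether or not a drug was started, so that the two sections agree.
4. Add a sensitivity analysis for 6-month values measured on a drug, using post-baseline values taken before the drug where the medical record holds them. Do not carry the baseline value forward. The visit descriptions retrieve HbA1c and OGTT at baseline and 6 months only, so for an early starter the last scheduled value may be baseline. Carrying it forward would record a progressor as having no change.

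The timing of the other five criteria should be left to the investigators. Kidney disease, for example, is excluded because of doubts about sensor accuracy, and that reason still applies at the 3-month sensor visit.

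The cost is a few sentences and one extra date per starter, since glycaemic outcomes are already traced from medical records. The downside is that some 6-month values will be measured on medication, which is why the sensitivity analysis is needed.

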3.2 Chrono-type and blood glucose homeostasis

Individual differences in the time at which people refer to do particular behaviors, most notably sleep, are referred to as chrono-type (Anothaisintawee et al. 2017). It is a behavioral manifestation of an individual's internal circadian clock system, which can be assessed with the use of multiple methodologies that classify individuals as having, e.g., a morning or an evening type (Gottlieb et al. 2015). Chrono-type is also used to describe personality traits associated with the preferred times-of-the-day for activities such as sleep or awake (Anothaisintawee et al. 2017). Generally, in the absence of environmental stimuli such as light, endogenous circadian clocks oscillate in a manner approximating a 24-hour cycle (Astiz et al. 2019). An individual's chrono-type is likely created by an interaction between the endogenous circadian pacemaker and its responses to light (Astiz et al. 2019) and can be modulated by factors such as age (Fischer et al. 2017) and life circumstance (e.g., needing to get to work early over years may shift preference towards earlier hours). In our modern society, night-shift work, which requires workers to eat and be active during their circadian night and sleep during their circadian day, represents an extreme form of circadian misalignment. A recent meta-analysis of 10 cohort studies (262294 participants) revealed that shift work was associated with a 40% increase in the risk of developing T2DM (Anothaisintawee et al. 2015). Recently, epidemiological and experimental studies have demonstrated that sleep quality and quantity are important determinants of whole-body metabolism. It has been suggested that impaired sleep might causally contribute to the T2DM (Sakamoto et al. 2018). Despite the clear association between short sleep and metabolic impairments, the underlying endocrine and molecular mechanisms remain only partially elucidated. Among the suggested mechanisms, the causal role of the hypothalamus-pituitary-adrenal (HPA) axis and sympathetic activation are supported by the largest body of literature. Circulating cortisol, assessed either by 24 h profiles or by single measurements of evening cortisol levels, were elevated together with markers of sympathetic activation and circulating catecholamine after total or partial sleep deprivation as well as in short sleepers (Reynolds et al. 2012). In contrast, some studies reported impairments in glucose homeostasis in sleep restricted individuals along with unchanged cortisol and catecholamine levels (Buxton et al. 2012). The complexity of associated endocrine mechanisms can be further demonstrated by observations of elevated levels of pro-inflammatory cytokines, lower circulating testosterone, decreased thyroid stimulating hormone levels and changes in adipokines secreted from adipose tissue in sleep deprivation (Froy & Garaulet 2018). Evening types (or late chrono-types) typically have later bedtime than those who are morning types (or early chrono-types). Those with later chrono-type usually experience a mild form of circadian misalignment due to a greater degree of misalignment between social rhythms and the circadian clock, a phenomenon called “social jetlag” (Fischer et al. 2017). In an individual presenting with

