pattern from the validated questionnaires PSIQ and light exposure from the validated questionnaire HLEQ.

Statistical Analysis

All data will be performed statistical analysis using the SPSS software version 20 (SPSS Inc., Chicago, IL, USA). The socio-demographic will be presented as mean, standard deviations, median, interquartile range, frequency, and percentage. Data cleaning will be performed to exclude the outlier data before the normality is checked using Kolmogorov-Smirnov Test. The investigator considered $p < 0.05$ to be statistically significant. Chronotype, sleep quality, and light exposure will be analyzed as categorical variables whereas dietary intake, chrononutrition, anthropometry, glycemic measure, and physical activity will be analyzed as continuous variables.

The investigator will perform a multivariable generalized linear model to examine the association between night meal pattern (last night mealtime either dinner or supper with calories intake, frequency of night snacking, and the total number of the night snacking) and glycemic outcome (HbA1c, FPG, 2hPPG, CGM profile) by adjusting for the potential covariates. Specifically, nighttime will be characterized by the time range from 1900 and 0659 hours based on Malaysia solar time. The investigator will explore the late-night meal timing in 2000, 2100, and 2200 to examine its association with glycemic outcomes. The potential confounders include sociodemographic characteristics, physical activity, sleep pattern, sedentary behavior, diet quality, and light exposure will be controlled. ANCOVA test will be performed to understand the association between chrononutrition (breakfast skipping, meal frequency, eating window, sleep timing, chronotype, and fasting pattern) with glycemic variables, controlling for potential covariates (sociodemographic characteristics, light exposure, diet quality, physical activity and sleep pattern).

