APPENDIX D
Munich Chronotype Questionnaire

8

9

Meal Timing and Glucose Tolerance

10

Project Name:

		/				/					11
d	d		m	m	m		y	y	y	13	12

13

14

15

16

Munich Chronotype Questionnaire (MCTQ)

17

18

This questionnaire requires you to report your sleep patterns over the past 4 weeks. Working day and non -working day sleep patterns were asked separately. Please answer this question according to your perceptions of your weekly habits, workday sleep patterns and non -working days.

[figure not shown]
23

I have regular working hours (this includes housewives):

24

 Yes, I work	 1	 2	 3	 4	 5	 6	 7		Day/week
 No									

If your answer is 'Yes, 7 days' or 'No', please consider whether your bedtime may differ between normal weekdays and weekends and fill out the MCTQ accordingly.

26

27

Based on the following picture, answer the question below (Please answer on a 24 -hour scale, for example; 23:00):

30

Working Days		
Picture 1	I entered the bedroom at: _____	
Picture 2	Some people stay awake even after lying in bed.	
Picture 3	I'm ready to go to bed at (turn off the lights and go to sleep): _____	
Picture 4	How many minutes do I need to sleep: _____	
Picture 5	I woke up in the morning at: _____	
Picture 6	I got out of bed after a few minutes: _____	
I use an alarm clock on weekdays		Yes  No
If YES, I usually wake up BEFORE the alarm clock rings:		Yes  No
Weekend		
Picture 1	I entered the bedroom at: _____	
Picture 2	Some people stay awake even after lying in bed.	

Picture 3	I'm ready to go to bed at (turn off the lights and go to sleep): _____			
Picture 4	How many minutes do I need to sleep: _____			
Picture 5	I woke up in the morning at: _____			
Picture 6	I got out of bed after a few minutes: _____			
My waking hours were due to the use of an alarm clock (Figure 5):		Yes		No

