There are certain reasons I can't determine my bedtime independently on holidays:		Yes		No
If 'Yes', among the factors are				
Child/husband/pet				
Hobby				
Solat/morning prayer/meditation				
Others (please state): _____				
Will I go back to sleep after doing the activity, on holidays?				
Yes		No		
If 'Yes' to the previous question, what time do you go to bed and wake up?				
Time to sleep again: _____				
Time to wake up again: _____				

31

32

33

34

35

36

37

38

39

40

41

42

43

44

45

46

47

48

49 Reference:

50

51 [name] Mazri, Zahara Abdul Manaf, Suzana Shahar, Arimi Fitri Mat Ludin, Norwahidah Abdul Karim,
 52 Andrea Yu-Lin Ban & Rose Azzlinda Osman (2021): Modified Munich chronotype questionnaire for application to
 53 short-interval split sleep of non-shift workers, Chronobiology International, DOI:
 54 10.1080/07420528.2021.1887209

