APPENDIX G
Havard Light Exposure Questionnaire

Project Name:

Meal Timing and Glucose Tolerance

Date of interview:

		/			/				
d	d		m	m	m	y	y	y	y

Date	Monday / Tuesday / Wednesday / Thursday / Friday / Saturday/ Sunday		
Time	Food & Beverage	Quantity	Note
Breakfast (: am)			
Morning Tea (: am)			
Lunch (: pm)			
Afternoon Tea (: pm)			
Dinner (: pm)			
Supper (: pm)			

116

117

118

119

120

121

122

123

124

125

126

127

128
 129

 130 **Harvard Light Exposure Assessment (H-LEA) Questionnaire**
 131 During a typical day, describe your exposure to the below specified light sources. Please fill in
 132 applies, for each single day of your 7 days trial and circle the hours at which you had a meal, like
 133 indicated in the example below.

 134 H=Halogen Lamp F=Fluorescent Lamp
 135 N=Natural Light (Indoors) S=Sunlight, Natural Light (Outdoors)
 136 O=Other Artificial Light Sources D=Darkness

Date:		
	Night Shift Workhours From	To
		139
	Day Shift Workhours From	To
		140
		141
	Off Work	142
Time	Exposure to Specified light sources	
1am		144
2am		145
3am		146
4am		147
5am		148
6am		149
7am		150
8am		151
9am		152
10am		153
11am		154
Noon		155
1pm		156
2pm		157
3pm		158
4pm		159
5pm		160
6pm		161
7pm		162
8pm		163
9pm		164
10pm		165
11pm		166
12pm		167
		168
		169
		170
		171
		172
		173

 174
 175

Reference:

Archna Bajaj, Bernard Rosner, Steven W. Lockley, and Eva S. Schernhammer. 2011. Validation of a Light Questionnaire with Real-life Photopic Illuminance Measurements: the Harvard Light Exposure Assessment Questionnaire. *Cancer Epidemiology Biomarkers Prevention*; 20(7): 1341–9.

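### Occasional night-shift workers stay eligible, and no model adjusts for night-shift work by name although the light-exposure form already records it

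*Combined protocol and SAP*

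**What the plan says.** **Eligibility.** In section 3 (Description of Methodology), the first exclusion criterion is "Night shift workers at least 3 times per week". No other criterion concerns shift work, so none, one or two night shifts a week is compatible with entry.

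**Background.** Literature review 3.2 treats night-shift work as an extreme form of circadian misalignment and reports that "shift work was associated with a 40% increase in the risk of developing T2DM". The end of 3.1.1 names it beside late-night feeding as a route to metabolic dysregulation.

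**Exposure.** Under Statistical Analysis, "nighttime will be characterized by the time range from 1900 and 0659 hours based on Malaysia solar time". The night-meal pattern (last night meal, frequency and number of night snacks) is related to HbA1c, FPG, 2hPPG and the CGM profile.

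**Covariates.** For the generalized linear model: "The potential confounders include sociodemographic characteristics, physical activity, sleep pattern, sedentary behavior, diet quality, and light exposure will be controlled". For the ANCOVA, which includes chronotype: "controlling for potential covariates (sociodemographic characteristics, light exposure, diet quality, physical activity and sleep pattern". The logistic regression of diabetes incidence on early or late-night mealtime lists no covariates.

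**Forms.** The chronotype form (Appendix D) opens with "I have regular working hours (this includes housewives", then has one block for working days and one for the weekend. Its cited source is a version for "short-interval split sleep of non-shift workers". The socio-demography form (Appendix B) asks job status and overtime after 7pm, but not shifts. The light-exposure form (Appendix G) has a field headed "Night Shift Workhours From". No analysis mentions that field.

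**The concern.** By the plan's own reasoning, night-shift work is tied to all three quantities under study: it moves eating into the night, disturbs the sleep times from which chronotype is scored, and worsens glucose control. That is the pattern of a confounder. The exclusion removes its frequent form and leaves the occasional form in, and the analysis does not name it. The resulting bias would run in the direction of the study hypothesis, which expects morning chronotype and early meals to go with lower glycaemia. A reader of a positive result could fairly ask whether part of it reflects who works nights.

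There is a separate measurement problem for chronotype. Someone who alternates day and night shifts has to report both kinds of working day in one set of answers, so the values mix two sleep schedules. Covariate adjustment does not repair that.

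**Working it through.** **1. Is there a gap in the text?**

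| Item | Where | Handles one or two night shifts a week? |
|---|---|---|
| Exclusion criterion 1 | Description of Methodology | No; applies from three a week |
| Generalized linear model covariates | Statistical Analysis | Not named; partly through sociodemographic factors (Table 4 lists occupation), sleep pattern and light exposure |
| ANCOVA covariates | Statistical Analysis | Same |
| Logistic model, mealtime and diabetes | Statistical Analysis | No covariates listed |
| Sleep pattern | Statistical Analysis, lifestyle models | Specified as sleep duration, which does not carry timing |
| Night-shift hours | Appendix G | Collected, not used in any analysis |

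The gap is real, and partial adjustment exists for the first two model families.

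**2. The plan's effect scale.** Inputs from Sample size Calculation: effect size 0.13, two-sided alpha 0.05, power 0.90, single regression coefficient. Using a noncentral t with noncentrality √(f² × N) and f² = 0.13, the required N is 83 for 1 to 7 predictors (84 for 10 to 15). This reproduces the stated 83, and 83/(1 − 0.5) = 166. So 0.13 entered the calculation as f². As a standardised slope it would give f² = 0.0169/(1 − 0.0169) = 0.0172 and N = 614.

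Implied difference between the later-eating and earlier-eating halves:
- partial r = √(0.13/1.13) = 0.339
- difference = 0.339 × 2√(2/π) = 0.339 × 1.596 = 0.54 SD (taking the exposure as roughly normal)

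**3. Illustrative bias.** Let p be the share of participants with occasional night shifts, d their glycaemic deficit in SD, and q the share of them in the later-eating half. Without adjustment:

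bias = 2p(2q − 1)d

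The documents give none of p, d or q; the values below are assumptions.

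| p | d | q | Bias (SD) | Share of 0.54 SD |
|---|---|---|---|---|
| 5% | 0.2 | 100% | 2 × 0.05 × 1 × 0.2 = 0.02 | 4% |
| 10% | 0.3 | 100% | 2 × 0.10 × 1 × 0.3 = 0.06 | 11% |
| 20% | 0.5 | 100% | 2 × 0.20 × 1 × 0.5 = 0.20 | 37% |
| 10% | 0.3 | 75% | 2 × 0.10 × 0.5 × 0.3 = 0.03 | 6% |
| 10% | 0.3 | 60% | 2 × 0.10 × 0.2 × 0.3 = 0.012 | 2% |

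With 83 evaluable participants split 41 and 42, the standard error of a half-versus-half difference is √(1/41 + 1/42) = 0.22 SD, so 0.06 SD is about a quarter of one standard error.

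**4. Cost of the remedy.** One added covariate leaves N at 83 to 84. Leaving shift workers out of a sensitivity run, with five predictors and f² = 0.13:

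| Share left out (assumed) | N kept | Power |
|---|---|---|
| 0% | 83 | 0.900 |
| 5% | 79 | 0.885 |
| 10% | 75 | 0.868 |
| 20% | 66 | 0.822 |

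**The case against.** The threshold of three shifts a week is a deliberate choice, and several stronger readings that a reader might draw do not survive the text.

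- *The chronotype form cannot be answered by shift workers.* It can. People without regular hours may say so and are told to complete the weekday and weekend parts accordingly. What stands is narrower: there is no separate place for shift-day sleep. The non-shift-worker point itself rests only on the title of the cited source.
- *On-shift meals are misclassified.* They are not. Night is defined by the clock, so a 02:00 meal is a night meal. The issue is confounding of a correctly measured exposure.
- *Nothing accounts for shift work.* Occupation, light exposure and sleep may absorb part of it, and the first covariate list need not be exhaustive. The illustrative bias above assumes no adjustment and is to that extent too high.
- *The 40% excess diabetes risk applies here.* The plan reports it for shift work in general, not for one or two nights a week.
- *The bias is about 29% of the target effect.* That follows only if 0.13 is a standardised slope (0.06/0.207). The sample size of 83 requires 0.13 to be f², which gives 11%.

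These objections shrink the point but do not remove it. Sleep duration does not capture timing, no text commits the analysis to coding shift work, and the logistic model has no listed adjustment at all.

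**Conclusion.** The point holds as a modest one. Occasional night-shift work is a plausible common cause of late eating, chronotype scores and glycaemia on the plan's own account. It is admitted by the eligibility rule, recorded on one form, and named in no model. The size of the bias cannot be derived from the documents. The illustration gives 0.06 SD, about 11% of the implied 0.54 SD, at 10% prevalence, a 0.3 SD deficit and every shift worker eating late. Across the other assumed values it runs from 0.012 to 0.20 SD (2% to 37%). Prevalence, deficit and placement are all assumptions, and existing covariates would lower the result. The documents do not support a claim that shift work would explain the main finding, or that eligibility or sample size must change.

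**What to change.** Leave eligibility and data collection unchanged. In the Statistical Analysis section:

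1. Derive any night-shift work (yes/no) from the night-shift hours on the light-exposure form.
2. Add it to the covariates of the night-meal generalized linear model and the chrononutrition and chronotype ANCOVA, and include it in the logistic model for mealtime and diabetes incidence.
3. Pre-specify one sensitivity analysis repeating the meal-timing and chronotype models without participants who report any night shift.
4. Report how many participants are affected, which would replace the assumed prevalence.

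The cost is one degree of freedom, one extra set of model runs, and slightly lower precision in the sensitivity run (power about 0.87 to 0.885 if 5% to 10% of 83 are left out).

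Two limits should be stated. The methods text describes the light-exposure form as covering a typical weekday and weekend day, whereas the form itself refers to each of seven days; if only typical days were recorded, some occasional shifts will be missed. A new visit item is not worth asking for: the document is dated 6 May 2024 and third visits were scheduled to end on 06/03/2024. Because analysis was scheduled from 07/03/2024, the wording should be fixed before the outcome models are run, or the additions labelled as post hoc.
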